### 4.2. Inclusion Criteria

To participate in the rollover protocol, each subject must meet *all* of the following inclusion criteria:

- Complete or have previously completed at least through the Week 96 Visit (*i.e.*, 96 weeks on study) for the FTC-203 study.
- Complete all End-of-Study Visit procedures for the FTC-203 study.
- Either (a) have a plasma HIV-1 RNA viral load of  $\leq 400$  copies/mL at the End-of-Study Visit for the FTC-203 study, or (b) if the subject's plasma HIV-1 RNA viral load at the End-of-Study Visit for FTC-203 study is  $> 400$  copies/mL, their viral load is  $< 1.0 \log_{10}$  above the nadir recorded after Week 8 of the FTC-203 study and there is reliable genotypic evidence showing a lack of resistance to emtricitabine.
- A parent or other legal guardian has provided written informed consent to the subject participating in the rollover protocol. As applicable, based on the subject's age and normal institution practice, the subject should additionally provide their written informed consent or assent to participate in the rollover protocol.
- If a female of childbearing potential has a negative serum beta-human chorionic gonadotropin ( $\beta$ -HCG) test at the End-of-Study Visit for the FTC-203 study.
- If sexually active (male and female) and/or of childbearing potential, be willing to use an effective method of contraception while enrolled in the study and for a period of at least 1 month after the last dose of emtricitabine. Acceptable methods of contraception include an intra-uterine device or barrier contraceptives (*i.e.*, cap/diaphragm, male condom, female condom, *etc.*) with a spermicide. Because the effects of emtricitabine on hormonal contraceptives have not been characterized, oral and depot contraceptives (*i.e.*, implant or injectable) must be used in conjunction with an acceptable barrier contraceptive. See Section 7.8 for more information on contraception and pregnancy.

- Have no medical condition or any other set of circumstances, which, in the opinion of the Investigator or Sponsor, means that it would not be in the best interests of the subject to participate in the rollover protocol and/or continue treatment with emtricitabine.

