### 7.3.                   **Serious Adverse Events**

A SAE is defined as follows:

Any adverse drug experience occurring at any dose that results in any of the following outcomes:

- Death;
- Life-threatening situation (subject is at **immediate** risk of death);
- In-patient hospitalization or prolongation of existing hospitalization (excluding those for study therapy or placement of an indwelling catheter, unless associated with other serious events);
- Persistent or significant disability/incapacity;
- Congenital anomaly/birth defect in the offspring of a subject who received study drug;
- Other: medically significant events that may not result in death, be immediately life-threatening, or require hospitalization, may be considered a SAE when, based upon appropriate medical judgment, they may jeopardize the subject and may require medical or surgical intervention to prevent one of the outcomes listed in this definition.

Examples of such events are:

- Intensive treatment in an emergency room or at home for allergic bronchospasm
- Blood dyscrasias or convulsions that do not result in hospitalization

- Development of drug dependency or drug abuse.

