#### **7.4.                   Serious Adverse Event Reporting Requirements**

##### **7.4.1.               All Serious Adverse Events**

GSI has requirements for expedited reporting of SAEs meeting specific requirements to worldwide regulatory authorities; therefore, GSI must be notified immediately regarding the occurrence of any SAE that occurs after the screening (initial) visit, including SAEs resulting

from study procedures performed from screening onwards. The procedures for reporting all SAEs, regardless of causal relationship, are as follows:

- Record the SAE on the AE CRF and complete the “Serious Adverse Event Report” form.
- Fax the SAE report to the attention of the GSI Global Drug Safety Department (GDS) within 24 hours of the Investigator’s knowledge of the event. GDS contact information is provided below.
- For fatal or life-threatening events, also fax copies of hospital case reports, autopsy reports, and other documents when requested and applicable.

GSI Global Drug Safety: Name:

PPD

Manager, GDS

Telephone:

PPD

(Working Days)

Fax:

PPD

Email:

PPD

GSI Medical Monitor:

Name:

[name].

Sr. Clinical Research Physician, Clinical Research

Telephone:

PPD

(Working Days) /

Cellphone:

PPD

(Medical Emergencies)

Fax:

PPD

Email:

PPD

GSI may request additional information from the Investigator to ensure the timely completion of accurate safety reports.

The Investigator must take all therapeutic measures necessary for resolution of the SAE. Any medications necessary for treatment of the SAE must be recorded onto the concomitant medication section of the subject’s CRF.

Follow-up of AEs will continue through the last day on study (including the follow-up, off study drug period of the study), until the Investigator and/or GSI determine that the subject’s condition is stable, or up to 30 days after the last dose of study drug, whichever is longer. GSI may request that certain AEs be followed until resolution.

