## 7.8. Risks for Women of Childbearing Potential or During Pregnancy

The risks of treatment with the study drug, emtricitabine, during pregnancy have not been evaluated. Animal studies do not indicate direct or indirect harmful effects of emtricitabine with respect to pregnancy. Please refer to the latest version of the Investigator's Brochure for additional information. Barrier contraception should always be used in combination with other methods of contraception (*e.g.*, oral or other hormonal contraceptives) by females of child bearing potential who are less than 2 years post-menopausal while participating in the study and for 30 days following the last dose of study drug. Male subjects in the study who are sexually active must use barrier contraception for the same period of time with their female partners of childbearing potential or agree to abstain from heterosexual intercourse for the duration of their participation in the study.

The subject must be instructed to discontinue the study drug (and other medications, as applicable) and inform the Investigator **immediately** if she becomes pregnant during the study.

The Investigator should report all pregnancies to the GSI within 24 hours of becoming aware of the pregnancy. The Investigator should counsel the subject regarding the possible effects of prior study drug exposure on the fetus and the need to inform the study center of the outcome of the pregnancy.

Any pregnancy complication or elective termination of a pregnancy for medical reasons will be recorded as an SAE. A spontaneous abortion is always considered to be an SAE and will be reported as described in the AE and SAE sections. Furthermore, any SAE occurring as an adverse pregnancy outcome post-study must be reported to GSI.

Additionally all pregnancies that occur during the study should be reported using the Pregnancy Report CRF page. Monitoring of the subject should continue until the conclusion of the pregnancy. The outcome should be reported to GSI using the Pregnancy Outcome (and Abnormal Pregnancy Outcome, if applicable) CRF page(s). If the end of the pregnancy occurs after the study has been complete, the outcome should be reported directly to GSI. Pregnancies that occur after the subject has discontinued study drugs do not require monitoring.

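### The waiver of pregnancy monitoring after drug discontinuation in protocol Section 7.8 does not fit the 30-day post-dose contraception window or the rule that pregnancies during the study are followed to conclusion

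*Protocol*

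**What the plan says.** Protocol Section 7.8 makes several statements that bear on a pregnancy close to the last dose.

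- **Contraception.** Females of childbearing potential are to use it "while participating in the study and for 30 days following the last dose of study drug". Section 4.2 sets the period as "for a period of at least 1 month after the last dose of emtricitabine".
- **First report.** "The Investigator should report all pregnancies to the GSI within 24 hours of becoming aware of the pregnancy". No limit to time on drug is stated.
- **CRF and follow-up.** The section says that "all pregnancies that occur during the study should be reported using the Pregnancy Report CRF page". The next sentence reads "Monitoring of the subject should continue until the conclusion of the pregnancy". An outcome falling after study completion goes directly to the sponsor.
- **Serious outcomes.** Pregnancy complications, terminations for medical reasons and spontaneous abortions are SAEs, and a serious adverse pregnancy outcome after the study must be reported.
- **Waiver.** The last sentence is "Pregnancies that occur after the subject has discontinued study drugs do not require monitoring". It makes no exception for the contraception window.

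Elsewhere, Section 7.3 lists as an SAE outcome "Congenital anomaly/birth defect in the offspring of a subject who received study drug". AE follow-up in Section 7.4.1 continues through the last day on study, until the subject is stable, or "up to 30 days after the last dose of study drug, whichever is longer". Section 7.4.3 asks for deaths within 30 days of the last dose.

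**The concern.** The contraception rule and the general post-dose safety rules look ahead 30 days from the last dose. Pregnancy monitoring alone stops at discontinuation. A conception on days 1 to 30 therefore falls in a period when the protocol asks subjects to avoid pregnancy, yet nobody is required to follow that pregnancy to its outcome.

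This matters because collecting long-term safety information is one of the study's two objectives, and Section 7.8 states that the risks of emtricitabine in pregnancy have not been evaluated. Passive reporting tends to bring in bad outcomes without the normal ones, so the few cases that arrive cannot be set against a known number of pregnancies. The parent study took subjects from 3 months to 17 years of age, and the SAP's visit windows run for about ten years, so girls can reach childbearing age during the rollover.

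**Working it through.** The documents give no sample size, rate or power figure on this point, so the check is a comparison of time windows and of instructions.

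**1. Overlap of the two windows**

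- Contraception window (Section 7.8): day 0, the last dose, to day 30. The 1 month in Section 4.2 is about the same length.
- Waiver (Section 7.8, last sentence): starts at discontinuation, day 0, with no end.
- Overlap: 30 of 30 days. No part of the contraception window carries an undisputed duty to follow a new pregnancy to conclusion.

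**2. What each pregnancy would receive under the current text**

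| Conception | Reported within 24 hours | Pregnancy Report CRF page | Followed to conclusion | Serious outcomes reportable |
|---|---|---|---|---|
| On drug | Yes | Yes | Yes | Yes |
| After last dose, still on study | Yes | Yes | Contradictory: the during-study sentence says yes, the waiver says no | Yes |
| Days 1 to 30 after last dose, off study | Yes | Not required | Waived | Yes, if the site learns of them |
| After day 30, off study | Yes, as worded | Not required | Waived | Yes, if the site learns of them |

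The second row can occur, because Section 7.4.1 itself refers to a period of the study spent off drug. The third row is the misalignment with the contraception window. The fourth row conflicts with neither the window nor the during-study sentence.

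**3. Can the boundary be applied?**

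The waiver turns on when a pregnancy occurs relative to stopping drug. Protocol Appendix 2 and SAP Appendix 1 schedule a pregnancy test only at the FTC-203 End-of-Study visit. Neither shows one at the 12-week visits or at Subject Discontinuation. Section 6.3 asks for AE assessment and drug accountability at discontinuation and does not mention pregnancy. A pregnancy recognised some weeks after stopping must therefore be dated without a protocol-scheduled test near the last dose, and one conceived shortly before that dose could be put on the exempt side by mistake.

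**4. Size**

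- Upper limit on subjects: 59, both sexes. The number of females of childbearing potential and the number of pregnancies are not given.
- Length of follow-up provided for: the last SAP window is Week 12 × 43 = 516 and closes on day 84 × 43 + 42 = 3,654. Dividing, 3,654 / 365.25 = 10.0 years.
- Effect on planned output: none. Neither protocol Section 8 nor the SAP names a pregnancy listing, and SAP Section 6.1 says AE details were collected only for AEs leading to study termination.

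**The case against.** Three stronger readings are tempting, and the documents support none of them.

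- **That these pregnancies yield no outcome data.** A reader might infer this from the waiver alone. But Section 7.8 asks for all pregnancies to be reported within 24 hours, has the subject counselled on telling the center the outcome, and makes complications, spontaneous abortions, medically indicated terminations and serious post-study outcomes reportable. Section 7.3 adds birth defects. The gap is in active ascertainment, mainly of non-serious outcomes.
- **That the rule drops pregnancies conceived on drug but recognised later.** The waiver concerns pregnancies that occur after discontinuation. On the ordinary meaning, one conceived on drug occurred earlier and must be followed. Only misclassification through uncertain dating remains as a risk.
- **That the protocol declares the 30 days a period of residual risk.** It gives no reason for the 30 days, and Section 7.8 says animal studies do not indicate harm. The AE follow-up rule in Section 7.4.1 is general and does not address pregnancy exposure. Residual risk is a possible inference, and the misalignment does not depend on it.

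It can also be said that data collection was narrowed on purpose, that a test at discontinuation could not detect a conception on the following days, and that some exits do not end exposure. Section 6.4 lists market approval where the subject can obtain the drug, and SAP Section 3.2 provides for rollover to another study whose rules are not visible here. These remarks are fair and limit the size of the point. They do not remove the contradiction for a subject off drug but on study, nor do they explain why the waiver begins 30 days before the contraception requirement ends.

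**Conclusion.** The point holds as a minor inconsistency. Followed exactly, the last sentence of Section 7.8 removes required active follow-up for every conception in the 30 days after the last dose, and for a subject still on study it contradicts the instruction earlier in the same paragraph. Initial reporting and SAE reporting remain. The loss is complete ascertainment: serious outcomes depend on the site hearing of them, and normal outcomes need not be captured.

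This rests on reading the word occur as referring to conception, and on there being at least some females of childbearing potential who stop drug. The number of pregnancies is unknown and likely to be very small. The value lies in individual safety cases, and no planned analysis figure changes.

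**What to change.** Reconcile the last sentence of Section 7.8 with the rest of that section and with Section 4.2, using the 30-day post-dose window the protocol already has. In substance:

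- Pregnancies conceived during the study, or within 30 days after the last dose, are followed to outcome on the existing Pregnancy Report and Pregnancy Outcome CRF pages.
- Where the conception date is uncertain, the pregnancy is treated as inside the window.
- Only conceptions after both the end of study participation and the 30-day window are exempt from monitoring.

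The 24-hour report and the SAE rules already stand and need no change. The amendment concerns data collection only and leaves dosing, treatment and contraception rules as they are. It also calls for no added pregnancy test, because the rule for uncertain dates deals with the dating problem.

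The cost is one rewritten sentence, with the submission and approval that a protocol modification requires, and outcome follow-up for a very small number of additional pregnancies.

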## **8. STATISTICAL CONSIDERATIONS**

No statistical analyses are planned. Data listings will be generated for all data collected in the clinical database. Listings will include subject enrollment/disposition, demographics (from the FTC-203 clinical database), SAEs, AEs leading to permanent discontinuation of study drug, emtricitabine, AEs associated with skin discoloration (hyperpigmentation), and study drug dispensing/accountability. Tabular summaries will be prepared.

## **9. RESPONSIBILITIES**

### **9.1. Investigator Responsibilities**

#### **9.1.1. Good Clinical Practice**

The Investigator will ensure that this study is conducted in full compliance with the principles of the “Declaration of Helsinki” (as amended in Edinburgh, Tokyo, Venice, Hong Kong, and South Africa), ICH guidelines, or with the laws and regulations of the country in which the research is conducted, whichever affords the greater protection to the study subject. For studies conducted under a US IND, the Investigator will ensure that the basic principles of “Good Clinical Practice,” as outlined in 21 CFR 312, subpart D, “Responsibilities of Sponsors and Investigators,” 21 CFR, part 50, 1998, and 21 CFR, part 56, 1998, are adhered to.

#### **9.1.2. Independent Ethics Committee Approval**

This protocol and any accompanying material to be provided to the subject (such as advertisements, subject information sheets, or descriptions of the study used to obtain informed consent) will be submitted, by the Investigator, to an independent ethics committee (IEC) and, where applicable, to the relevant regulatory and/or health authorities in each respective country. Approval from the IEC and, where applicable, the relevant regulatory/health authority(ies) must be obtained **before** starting the study and should be documented in a letter to the Investigator specifying the protocol number, protocol version, documents reviewed, and date on which the IEC met and granted the approval.

Any modifications made to the protocol after receipt of IEC approval must also be submitted to the IEC and, where applicable, the relevant regulatory/health authority(ies) for approval prior to implementation.

#### **9.1.3. Informed Consent**

It is the responsibility of the Investigator to obtain written informed consent from each individual participating in this study after adequate explanation of the aims, methods, objectives, and potential hazards of the study and prior to undertaking any study-related procedures. The Investigator must utilize an IEC-approved consent form for documenting written informed consent. Each informed consent will be appropriately signed and dated by the subject or the subject’s legally authorized representative and the person obtaining consent.

#### **9.1.4. Confidentiality**

The Investigator must assure that subjects’ anonymity will be strictly maintained and that their identities are protected from unauthorized parties. Only subject initials and an

identification code (*i.e.*, not names) should be recorded on any form submitted to the Sponsor and IEC. The Investigator must keep a screening log showing codes, names, and addresses for all subjects screened and for all subjects enrolled in the trial.

The Investigator agrees that all information received from GSI, including but not limited to the Investigator's Brochure, this protocol, CRFs, the investigational new drug, and any other study information remain the sole and exclusive property of GSI during the conduct of the study and thereafter. This information is not to be disclosed to any third party (except employees or agents directly involved in the conduct of the study or as required by law) without prior written consent from GSI. The Investigator further agrees to take all reasonable precautions to prevent the disclosure by any employee or agent of the study site to any third party or otherwise into the public domain.

#### **9.1.5. Study Files and Retention of Records**

The Investigator must maintain adequate and accurate records to enable the conduct of the study to be fully documented and the study data to be subsequently verified. These documents should be classified into two separate categories (although not limited to) the following: (1) Investigator's study file, and (2) subject clinical source documents.

The Investigator's study file will contain the protocol/amendments, CRF and query forms, IEC and governmental approval with correspondence, informed consent, drug records, staff curriculum vitae and authorization forms, and other appropriate documents and correspondence.

Subject clinical source documents (usually defined by the project in advance to record key efficacy/safety parameters independent of the CRFs) would include (although not, limited to) the following: subject hospital/clinic records, physician's and nurse's notes, appointment book, original laboratory reports, electrocardiogram, electroencephalogram, X-ray, pathology and special assessment reports, consultant letters, screening and enrollment log, *etc.*

All clinical study documents must be retained by the Investigator until at least two years after the last approval of a marketing application in an International Conference on Harmonization (ICH) region (*i.e.*, US, Europe, or Japan) and until there are no pending or contemplated marketing applications in an ICH region; or, if no application is filed or if the application is not approved for such indication, until two years after the investigation is discontinued and regulatory authorities have been notified. Investigators may be required to retain documents longer if required by applicable regulatory requirements or an agreement with GSI. The Investigator must notify GSI Sciences prior to destroying any clinical study records.

Should the Investigator wish to assign the study records to another party or move them to another location, GSI must be notified in advance.

If the Investigator cannot guarantee this archiving requirement at the study site for any or all of the documents, special arrangements must be made between the Investigator and GSI to

store these in sealed containers outside of the site so that they can be returned sealed to the Investigator in case of a regulatory audit. Where source documents are required for the continued care of the subject, appropriate copies should be made for storage outside of the site.

#### **9.1.6. Case Report Forms**

For each subject enrolled, a CRF must be completed and signed by the Investigator or Sub-investigator within a reasonable time period after data collection. This also applies to records for those subjects who fail to complete the study. If a subject withdraws from the study, the reason must be noted on the CRF. If a subject is withdrawn from the study because of a treatment-limiting AE, thorough efforts should be made to clearly document the outcome.

#### **9.1.7. Drug Accountability**

The Investigator or designee (*i.e.*, pharmacist) is responsible for ensuring adequate accountability of all used and unused study drug. This includes acknowledgment of receipt of each shipment of study product (quantity and condition) and subject dispensing records and returned or destroyed study product. Dispensing records will document quantities received from GSI and quantities dispensed to subjects, including lot number, date dispensed, subject identifier number, subject initials, and the initials of the person dispensing the medication.

At study initiation, the monitor will evaluate the site's standard operating procedure for study drug disposal/destruction in order to ensure that it complies with GSI requirements. Drug may be returned or destroyed on an ongoing basis during the study if appropriate. At the end of the study, following final drug inventory reconciliation by the monitor, the study site will dispose of and/or destroy all unused study drug supplies, including empty containers, according these procedures. If the site cannot meet GSI's requirements for disposal, arrangements will be made between the site and GSI or its representative, for destruction or return of unused study drug supplies.

All drug supplies and associated documentation will be periodically reviewed and verified by the study monitor over the course of the study.

